3.2.1 Primary outcomes

Primary outcomes will be the change in bacterial load compared to baseline. (see appendix A – molecular microbiology protocol for details on quantification). [name] laboratory at UM Miller School of Medicine, Department of Dermatology and Cutaneous Surgery will be the coordinating center responsible for tissue sample receipt and

processing. Bacterial load in CFU/g among treatment and control arms will be calculated for each wound at visits T0, T2 and T3. The trajectories of bacterial load for each subjects and average change in bacterial load between groups will be compared.

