6.3 Handling missed visits

It is preferred that subjects are seen at regular intervals. However, this may not be possible at times. If a subject needs to miss a visit, every effort should be made to reschedule as close as possible to the original date and then resume following visits at the original intervals. For example, if a subject regularly visits on Wednesdays and will miss a visit and a makeup visit is scheduled for that Friday, the next visit should return to the original intervals and be scheduled for the next Wednesday.

6.4 Stopping rule:

The PI may decide to stop the trial due to safety concerns at any time during the trial. The PI may consult the local Institutional Review Board (IRB) and/or Sponsor for safety related decisions.

7 Statistical methods

This study is a single center randomized longitudinal pilot study to investigate the effectiveness of Cutimed® Sorbact® (Study Device) compared to Comparator (silver impregnated contact layer dressing - Acticoat®) in modifying bacterial load in venous leg ulcers (VLU). Efficacy will be measured as the difference in change in bacterial load compared to baseline between two study arms i.e. Study Device vs. Comparator. This study will also

compare bacterial silver resistance based on genetic and phenotypic characterization over time, healing rate, complete healing at 6 weeks, pain, quality of life (QOL) measurements and adverse events as secondary endpoints.

We expect to study n=30 subjects for both the primary and secondary endpoints. The number of subjects estimated for the study (n=30) is not based on hypothesis driven statistical power calculation. Rather, as a pilot study, a goal for this investigation is to generate effect estimates that will assist in determining an appropriate sample size for future studies.

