Prior to performing statistical analyses on quantitative study data, the data will be checked, screened and verified to ensure the integrity of the database. Data screening will focus on several aspects. We will determine the amount, the pattern, and randomness of missing data. We will define outliers as observations that appear to be very high or very low, and decide how to proceed based on the presumed cause. We will identify inconsistencies within a single variable and between variables. Initially, we will perform an explanatory data analysis; visually via graphics/plots and numerically by descriptive statistics with mean, standard deviation for measurements taken on a continuous scale, and frequencies and percentages, various types of cross-tabulations for measurements taken on a categorical scale. Corresponding confidence intervals (CI) for means and proportions will be calculated. To have a better understanding of the relationships among different study measurements, parametric or non-parametric correlation coefficients, bivariate/multidimensional cross-tabulations will be constructed. All the descriptive statistics will be reported for all subjects and by study arm.

The primary endpoint of the study, the bacterial load in CFU/g, will be calculated for each wound at visits T0, T2 and T3 among Study Device and Comparator arms. The difference in means of the bacterial load from T3 to T0 will be calculated and compared between study arms with Student's t-test. To be able to study the trajectories of the bacterial load over time, overall and by study arms, the time series plots will be depicted and repeated measures regression analysis will be performed where time and study arm as the main effects. Types of variance-covariance matrix will be determined by standard statistical procedures. We plan to expand the regression model and include other subject characteristics for additional covariate adjustment. Adjusted regression coefficients and corresponding 95% confidence interval (95%CI) will be reported for the study arm as the main effect in the regression models.

The secondary endpoints such as microbiological outcomes, clinical wound outcomes, pain related outcomes, quality of life measurements, and safety outcomes will be analyzed with similar statistical methods as the primary endpoint.

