Due to the nature of a pilot study with limited sample size, regression models might have convergence problem i.e. regression estimates and corresponding 95%CI might not be estimable.

Therefore, we might explore different regression models as a secondary source of modeling approach. Regression model assumptions will be checked and model diagnostics will be done based on the appropriate statistical tools. Transformations of the data in order to meet statistical assumptions will be undertaken when indicated. Type-1 error will be set to 5% (alpha=0.05) and will be adjusted for multiple comparisons. Standard model diagnostic tools will be used. All of the statistical analyses will be carried out using SAS (SAS Institute Inc., Cary, NC) or R (R Foundation for Statistical Computing, Vienna, Austria. <http://www.R-project.org/>).

8 Regulatory and ethical issues

8.1 protocol institutional approval

The PI will submit the protocol and all related materials (e.g. ICF) for approval by the local Institutional Review Board (IRB) before any study related activity commences. All local and Federal regulatory rules will be followed and a dedicated regulatory monitor will be assigned to the protocol.

8.2 informed consent

During visit S1 and before any study activities are initiated, each subject will be provided with detailed information about the study and ample time to review ICF in order to obtain an informed consent. The subject (or legally authorized representative) will then be given the opportunity to ask any questions about the study and all questions will be answered. The subject (or legally authorized representative) will then sign and date the ICF according to the regulatory and legal requirements. ICF will be signed, dated and retained by the PI as part of the study records. No study related activities or procedures will take place before valid consent is obtained in an ethical manner and without.

In the case of a protocol amendment, the ICF will be revised to reflect said changes as required by IRB. Once revised, the ICF will be signed by all new subjects enrolled from that date forward as well as for all subjects still in the study (i.e. in the screening, treatment or follow up phase) when they are next scheduled to appear for a study visit.

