VLU debrided tissue will be collected from patients at the initial clinic visit (T0) and at routine follow-up visits (T2 and T3). Collected tissue will be measured and immediately after preserved at -80°C. DNA will be extracted from all samples using a solvent and grinding DNA extraction protocol (Bacterial/Fungal DNA isolation kit-Zymo Research). DNA quality and quantity control will be assessed by Real-Time PCR (qPCR) and Quant-It PicoGreen assay (Life Technologies), respectively. All of the methods required for DNA isolation and analysis are well established in [name] laboratory [32]; [33]; [34]. Quantification of all bacterial species in wound samples will be performed based on PCR amplification of 16S rRNA gene. The 16S rRNA gene (rDNA) is a DNA segment in all bacteria and archaea that codes for a structural RNA component of the small ribosomal subunit. The 16S rDNA is commonly used to quantify bacteria from human wound samples. We will employ 16S rDNA multiple hypervariable region to accomplish microbial quantification in VLU. Specifically, the 16S rDNA V1-V3 variable regions will be PCR

amplified to enrich the samples using the degenerate forward 27F.1 and non-degenerate reverse 518R primers that consist of sequences flanking the conserved hypervariable region. Separate PCR reactions will be prepared for each sample, including positive PCR control, and no template control. Real-time PCR will be performed and data will be analyzed using standard procedures established in [name] laboratory. Standard graphs will always be prepared from data accumulated at the same time as the test samples to act as internal controls. All qPCR reactions will be done in triplicate using the CFX96 real-time PCR system (Bio-Rad) and the PerfeCTa SYBR Green SuperMix (Quanta BioSciences). The relative CFUs will be calculated based on the standard curve. Assay results will be expressed as threshold cycle number (Ct) of the 16S rRNA gene copies per sample and tissue mass (mg). Standard curve will be used to determine relative CFUs based on Ct. Relative CFUs for tissue at two-weeks post initial treatment application (T2), and three weeks post treatment application (T3, if the percentage area reduction did not reach 75%). This qPCR based approach allows detection of bacteria which are difficult to cultivate and that would in all practicality remain undetected or underestimated by standard culture microbiology methods.

DNA standards for determining bacterial number by qPCR

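### The primary test of bacterial load defaults to raw CFU/g change, may be moved to another unnamed scale after the data are seen, and does not adjust for T0 load

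*Combined protocol and SAP*

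**What the plan says.** Section 7 gives the primary endpoint as bacterial load in CFU/g at T0, T2 and T3, and names the test: "The difference in means of the bacterial load from T3 to T0 will be calculated and compared between study arms with Student's t-test". Section 3.2.1 is no more specific about scale: "The trajectories of bacterial load for each subjects and average change in bacterial load between groups will be compared".

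A supporting analysis is also planned: "repeated measures regression analysis will be performed where time and study arm as the main effects". It may be extended: "We plan to expand the regression model and include other subject characteristics for additional covariate adjustment". These characteristics are not listed, and T0 load is not named among them.

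On assumptions, Section 7 says "Regression model assumptions will be checked and model diagnostics will be done based on the appropriate statistical tools" and then "Transformations of the data in order to meet statistical assumptions will be undertaken when indicated". No transformation, test or threshold is given.

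Appendix A derives load from qPCR: "Standard curve will be used to determine relative CFUs based on Ct". It summarises the resulting CFU/g by mean and SD at each time point. The only explicit log scale in the documents, Log CFU/g in the last part of Appendix A, is attached to colony counts for the MIC work, not to the qPCR load.

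Section 7 makes no power claim. It says that "a goal for this investigation is to generate effect estimates that will assist in determining an appropriate sample size for future studies".

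**The concern.** Two separate matters are involved.

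**Scale.** Bacterial counts usually span orders of magnitude, and a t-test on raw differences is then driven by the few largest wounds. The plan has a default (raw CFU/g) and an open permission to leave it. The scale decides the question answered: raw CFU/g compares arithmetic mean changes, while log10 compares geometric mean ratios. If the switch is made on inspection of the data, the data help choose the estimand. The mechanics are also unstated. A T3 minus T0 difference is negative wherever load falls, so it cannot itself be logged; the log must be taken of each load before subtraction.

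**Baseline.** Subtracting T0 is not the same as adjusting for it. When T0 and T3 are imperfectly correlated, subtraction brings in T0 noise that a regression on T0 would remove, and it overcorrects when the arms differ at T0 by chance.

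Both bear on the stated goal. In a pilot meant to produce effect estimates, the estimate and its SD are the product.

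**Working it through.** **Inputs from the documents.** 15 completers per arm (Section 4.1; Section 7 gives n=30); T0 and T3 load; alpha 0.05 (sidedness not stated, taken as two-sided). The sample size is expressly not a power calculation, so there is no power figure to reproduce. No SD, correlation or effect for load is given.

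**Assumed inputs.** Log-normal load with log10 mean 6; log10 SD 0.5, 0.7, 1.0 or 1.3; T0-T3 correlation r of 0.3 or 0.5; a fall common to both arms of 0 or 0.5 log10; a true device advantage of 1 log10. That makes 16 scenarios of 20,000 simulated trials each.

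**Step 1, scale.** Ranges over the 16 scenarios:

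| Analysis | Wrong-sign estimate | Power |
|---|---|---|
| Raw CFU/g change, t-test | 5-39% | 2-44% |
| log10 change, t-test | 0-4% | 41-100% |
| log10 ANCOVA on log10 T0 | 0-2% | 55-100% |

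The best raw result (44%) needs SD 0.5, r = 0.5 and no common fall. With a common fall of 0.5 log10 the raw wrong-sign rate is 27-39%.

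**Step 2, what the transformation clause recovers.** One plain reading is a Shapiro-Wilk test on the raw-change residuals, followed by log10 change if p < 0.05. This gives a wrong sign in 0-4%, power at most 3.5 points below log10 change, and false positives of 4.3-6.1%. The trigger is assumed, and it matters to how often the scale switches: 88-100% of pilots with Shapiro-Wilk, 67-95% with an absolute skewness above 1. Taking the better of the raw and log10 p-values gives 5.5-7.1% false positives.

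**Step 3, T0 covariate, equal SDs.** With log10 SD s at both visits, the variance of a change is 2s²(1 - r) and the residual variance given T0 is s²(1 - r²). The ratio is (1 - r²) / [2(1 - r)] = (1 + r)/2, which is 0.65, 0.75 and 0.85 at r = 0.3, 0.5 and 0.7. Simulated at 15 per arm it is 0.67-0.79 for r of 0.3 to 0.5, slightly less favourable because the T0 slope is estimated.

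At SD 1.0, simulated power rises from 61% to 78% at r = 0.3 and from 75% to 85% at r = 0.5. The median 95% CI half-width falls from about 0.87 to 0.72 log10 and from 0.74 to 0.65 log10.

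**Step 4, unequal SDs.** With k = SD(T3)/SD(T0), the ratio is k²(1 - r²) / (1 + k² - 2rk):

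| k | r = 0.3 | r = 0.5 | r = 0.7 |
|---|---|---|---|
| 0.8 | 0.50 | 0.57 | 0.63 |
| 1.0 | 0.65 | 0.75 | 0.85 |
| 1.25 | 0.78 | 0.89 | 0.98 |
| 1.5 | 0.87 | 0.96 | 1.00 |

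The gain can be large or almost nil. Asymptotically the ratio does not exceed 1.

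**Step 5, chance imbalance.** The standard error of the T0 difference between arms is s × √(2/15), or 0.365 at SD 1.0. The probability of a difference above 0.5 log10 in either direction is 17% (0.6% at SD 0.5, 29% at SD 1.3). With equal SDs such an imbalance shifts the change-score estimate by (1 - r) × 0.5, which is 0.25 log10 at r = 0.5.

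**The case against.** The sponsor can fairly say that the trial is exploratory and claims no power, that Section 7 already provides for checking assumptions and transforming, and that any analyst would log bacterial counts. On the figures above, that route recovers nearly all of the scale loss, and even picking the better p-value inflates the false-positive rate only modestly. This stands, and it limits the scale point to an avoidable ambiguity. Two gaps remain: the transformation sentence follows one about regression models and does not mention the t-test, and it says nothing of baseline adjustment.

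A reader might infer more than the documents support:

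- *That the plan has no scale or estimand until the data arrive.* It has one: raw CFU/g change. The fault is that it may be changed by an unstated rule.
- *That omitting T0 changes the estimand or biases the trial.* On a fixed scale in a randomised comparison it does neither. The cost is precision and control of chance imbalance.
- *That the primary analysis will have almost no power.* That holds only if it is run untransformed on strongly skewed data.
- *That the next trial would be sized wrongly.* Its size depends on its own analysis, which may use ANCOVA whatever is done here. Appendix A promises the raw qPCR data to the sponsor, and Section 7 plans correlations among measurements, so the planning quantities can be recovered.

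The Log CFU/g in Appendix A is no answer, since it concerns culture counts. Nor is Ct, which Appendix A reports but does not make the scale of the primary comparison.

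**Conclusion.** The gap is real and worth closing, but moderate. On the text, the primary comparison has a raw-scale default, an open-ended permission to change it, and no T0 covariate.

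The damage from scale is serious only if the default is kept on roughly log-normal data. If the transformation clause leads to log10, what is left is an estimand not fixed in advance. The loss from omitting T0 is not repaired by that clause. Its size depends on the T0-T3 correlation and on the ratio of the two SDs: ANCOVA variance is roughly 0.50 to 1.00 of the change-score variance over the ranges examined.

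All figures rest on assumed distributions, SDs, correlations and effect, and on 15 usable T3 values per arm. Appendix A makes the T3 load conditional on area reduction not having reached 75%. Absent T3 values are a separate issue, which neither this finding nor its remedy settles.

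**What to change.** In Section 7:

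1. Name log10(CFU/g) from qPCR as the primary scale, with the log taken of each load.
2. Replace the change-score t-test with ANCOVA of log10 T3 on arm with log10 T0 as covariate. Alternatively, use a repeated measures model of T2 and T3 with log10 T0 as covariate and an arm-by-time term, reading the arm contrast at T3.
3. Report the ratio of geometric means with its 95% CI. For planning, also report the log10 SDs at T0 and T3 and their correlation.
4. State how values below detection are handled. A log scale requires this rule, so it is not optional.
5. Keep CFU/g as a descriptive summary, and limit the transformation clause to sensitivity analyses for this endpoint.

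The cost is a few sentences and no new data, since T0 load is already measured. The covariate uses one degree of freedom, and the result becomes a fold change instead of an absolute difference in CFU/g. The change should be made before the laboratory and the analysis are unblinded.

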3. STUDY DESIGN

3.1 Overview:

This is an exploratory, single center, observer masked, active control, 1:1 randomized clinical trial. The goal is to compare the effectiveness of Study Device (Cutimed® Sorbact® wound contact layer) to an active control (silver contact layer Acticoat®). Both devices are already approved and indicated for treatment of wounds. Standard care selected for use in this trial includes sharp debridement and compression with Jobst Comprifore® 4 layer compression system.

The study consists of three phases: two weeks screening phase (phase-1), up to four weeks treatment phase (phase-2), and two weeks follow up phase (phase-3).

In the screening phase i.e. phase-1, the Investigators will choose Study Ulcer, make baseline measurements and assessments and verify inclusion and exclusion criteria are met. Standard care will be applied without use of Study Device or active control.

The treatment phase i.e. phase-2 may last up to four weeks (if healing did not occur prior) and includes application of study dressings as well as application of standard care and measurements of primary and secondary outcomes. This will be achieved by tissue collection procedures conducted at visits T0, T2, and T3. [name] and her research team will conduct the molecular microbiology and standard microbiology assessments of the specimens collected in this study. Gene expression (by qPCR) and standard microbiology will be utilized to characterize the mechanisms through which Cutimed® Sorbact® changes the bacterial load and promotes healing of chronic venous leg ulcers. Understanding the mechanism through which Cutimed® Sorbact® stimulates healing in patients may promote, improve and expand its clinical use.

In the two weeks follow up phase i.e. phase-3 subjects will return for one visit and secondary outcomes will be assessed and standard care provided. The subjects will then be discharged from the study and return to their wound care provider for further management as indicated.

3.2 Study outcomes:

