4.1 Overview

Subjects for the study will be recruited from the University of Miami (UM) patient population as well as other patients referred to UM for the study. The recruitment goal for this pilot study is 30 subjects. Considering up to 15% drop out rate, the study will enroll up to 35 subjects with the goal of having 15 subjects in each arm complete the study.

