4.4 Definition of study completion

A subject will be considered as completed the study if:

1. Subject healed during the treatment or follow up phase and completed all visits in the follow up phase.
2. Subject did not heal and completed all visits in the treatment and follow up phase.
3. Subject healed and then wound recurred and completed the follow up phase.

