5.16 Tissue collection

Tissue collection will be conducted at visits T0, T2 and T3 as per appendix A. All collection containers are pre-labeled with the subject ID. After collection, the date is written on the container label.

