5.21 Instructions for follow up care

Once subjects are identified as healed, they will move into the follow up phase. Subjects who completed the treatment phase (regardless of healing status) will be moved to the follow up stage as well. While in the follow up phase, subjects will be returned to the care provider who referred them to the study and follow up care will consist of appropriate compression therapy, wound care (if needed) and other medically indicated treatments as determined by the PI.

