This research protocol will provide information that may further the understanding of Cutimed® Sorbact® treatment in accelerating wound healing via changes in microbial load and prevention of silver resistance. The bacterial load is increased in non-healing

VLU and promoting a non-healing wound phenotype. We will also evaluate expression of specific set of silver resistance genes whose expression may be stimulated by prolonged Ag-based therapy. [14]

Tissue Collection Procedure

Debridement tissue samples will be taken from the edge of the wound and will be taken at the initial visit and 2 additional points during the trial. The tissue will be transported in a sterile container on ice to [name] lab immediately after collection. One half of the tissue will directly stored into -80°C freezer for DNA isolation; the second half will be preserved in 80% glycerol for colony isolation using standard microbiology and analyzes of silver resistance on phenotypic level. The initial tissue removed will be considered the baseline and will be noted as T0.

Time Point Definitions

T0 – Pre-Randomization

T2 – Two weeks post-initial application SOC+ Cutimed® Sorbact® or SOC + Acticoat®

T3 – Three weeks post-initial application SOC+ Cutimed® Sorbact® or SOC + Acticoat®

DNA Isolation and qPCR

High bacterial burden ($>10^5$ organisms per gram of tissue), even without the classic signs of infection, is detrimental to healing [1, 10, 29]. Bacteria are routinely isolated from VLU by culturing methods. However, standard microbiology techniques present barriers to accurate microflora quantification because many of the chronic wound bacteria are recalcitrant to growth in a culture and are therefore difficult to identify in this manner [30]; [31]; [1]. The availability of molecular PCR based methods has provided researchers with the capability to examine the bacterial composition of human tissue samples in unprecedented detail. This approach would be utilized to further our understanding of mechanism of action Cutimed® Sorbact® on bacterial populations in VLU.

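### Ulcers that close by T3 have no T3 load for the primary T3-T0 t-test, yet count as completers toward 15 per arm, and Section 7 has no rule for them

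*Combined protocol and SAP*

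**What the plan says.** - **Primary test.** Section 7: "The difference in means of the bacterial load from T3 to T0 will be calculated and compared between study arms with Student's t-test". Section 3.2.1 promises the measurement for every wound: "Bacterial load in CFU/g among treatment and control arms will be calculated for each wound at visits T0, T2 and T3".
- **Sampling.** Section 5.16: "Tissue collection will be conducted at visits T0, T2 and T3 as per appendix A". Appendix A, Tissue Collection Procedure: "Debridement tissue samples will be taken from the edge of the wound". Table 1 shows no tissue collection at T4 or F1.
- **What happens at healing.** Section 3.1 ends the treatment phase early if the ulcer heals, and 5.21 adds: "Once subjects are identified as healed, they will move into the follow up phase". Follow-up is a single visit.
- **Who is a completer.** Section 4.4, item 1: "Subject healed during the treatment or follow up phase and completed all visits in the follow up phase". No T3 sample is required.
- **Target.** Section 4.1: "the study will enroll up to 35 subjects with the goal of having 15 subjects in each arm complete the study". Section 7 expects 30 subjects for the primary as well as the secondary endpoints.
- **Missing data.** Section 7 says that the amount, pattern and randomness of missing data will be examined. It gives no rule for healed ulcers.
- **A further condition.** Appendix A, under DNA Isolation and qPCR, attaches a condition to the T3 value: area reduction must not have reached 75%. Sections 3.2.1, 5.16 and 7 do not carry this condition.

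**The concern.** A change-score t-test needs both values. If the T3 value cannot exist once the ulcer has closed, subjects leave the primary comparison because of something that happened after randomisation and that treatment may influence. The groups compared are then no longer the randomised groups.

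This matters even though the trial makes no power claim. Section 7 says that the purpose is to generate effect estimates for sizing later studies, so a distorted difference or SD affects the main product of the pilot. There is also a counting problem: the 15 per arm in 4.1 are completers, while the primary test needs T0-T3 pairs. Nothing in the plan replaces a completer who has no pair.

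**Working it through.** **1. Trace a healed subject through the visits** (Table 1, 5.16, 5.21, Appendix A).

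| Ulcer first found closed at | Load values available | In T3-T0 t-test? | Completer under 4.4 if F1 attended? |
|---|---|---|---|
| T1 or T2 | T0 only | No | Yes |
| T3 | T0, T2 | No | Yes |
| T4 or later | T0, T2, T3 | Yes, unless the 75% condition removes T3 | Yes |

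**2. Reproduce the plan's figure.** Section 4.1 goes from 30 completers and 15% dropout to 35 enrolled. 30/(1 - 0.15) = 35.3 and 30 x 1.15 = 34.5, so 35 is reproduced to within rounding (35 x 0.85 = 29.75). The whole allowance is used by dropout; none is left for completers without T3 tissue.

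**3. Expected number of pairs.** Let h be the share of completers without T3 tissue. The documents do not give h; 5%, 10% and 20% are assumptions.

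- Pairs among 30 completers, 30(1 - h): 28.5, 27, 24.
- Chance that at least one of 30 lacks T3, 1 - (1 - h)^30: 0.785, 0.958, 0.999.

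**4. Precision.** The 95% CI half-width for the arm difference, in SD units, is t(0.975, 2n - 2) x sqrt(2/n).

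- n = 15: 2.048 x 0.365 = 0.75
- n = 14: 0.78
- n = 13: 0.81
- n = 12: 2.074 x 0.408 = 0.85, which is 13% wider than at 15 (0.847/0.748 = 1.13)

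**5. Bias, as an illustration only.** Let load reduction have SD 1, with mean 0 in Comparator and 1 in Study Device. Let a latent healing score have correlation r with load reduction, and let its mean be shifted by r x 1 in the Study Device arm, so that treatment acts on healing only through load. T3 is missing when the score exceeds c, where c is set by the assumed share missing in Comparator. The means among subjects with T3 are:

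- Comparator: -r x phi(c)/Phi(c)
- Study Device: 1 - r x phi(c - r)/Phi(c - r)

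Worked case, r = 0.5 and 10% missing in Comparator: c = 1.282. Comparator mean = -0.5 x 0.1755/0.900 = -0.0975. Study Device mean = 1 - 0.5 x 0.2939/0.7828 = 0.8122. Difference = 0.910, an attenuation of 9%.

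| r | Missing, Comparator | Missing, Study Device (implied) | Observed difference (SD) | Attenuation |
|---|---|---|---|---|
| 0 | 10% | 10% | 1.00 | 0% |
| 0.3 | 5% | 9% | 0.98 | 2% |
| 0.3 | 20% | 29% | 0.96 | 4% |
| 0.5 | 10% | 22% | 0.91 | 9% |
| 0.7 | 5% | 17% | 0.86 | 14% |
| 0.7 | 10% | 28% | 0.81 | 19% |
| 0.7 | 20% | 44% | 0.75 | 25% |

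The last row needs 44% of Study Device ulcers to lack T3, so it is an outer bound rather than an expectation.

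**6. Does the repeated measures model already cover this?** Section 7 introduces it to study trajectories and names time and arm as main effects only. Without an arm-by-visit term the two trajectories are forced to be parallel. The arm coefficient is then an average difference over visits, not a difference in change at T3.

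**The case against.** The case on the other side has several parts.

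- **Few ulcers may close in three weeks.** Subjects have persistent, previously silver-treated ulcers, and exclusion criterion 2 in 4.3 removes ulcers whose area changed by more than 30% before treatment. At 5% the expected loss is 15 x 0.05 = 0.75 subjects per arm. This stands: the rate is unknown and may be low.
- **The direction is not established.** A reader might infer that the test discards the subjects with the largest fall in load and so understates the Study Device. The documents do not support this. Appendix A says that high load impairs healing, which concerns level and not change. Early healers may have started with low load and had less room to fall, or may simply have had small ulcers. If more ulcers closed on Study Device and those had the smaller falls, the effect would be overstated.
- **The effect need not vanish.** A reader might also construct a case in which the whole difference disappears: 20% versus 7% heal, each healed ulcer falls 2 log10 and every other ulcer in both arms falls 0.5. The all-subject difference is then 0.800 - 0.605 = 0.195, and the difference among remaining wounds is 0. That zero is built in by giving non-healers in both arms the same fall. If Study Device non-healers fall 1.0 instead, the figures are 1.200 - 0.605 = 0.595 against 0.500 observed, about 16% attenuation.
- **It overlaps with the 75% condition.** A closed ulcer has 100% area reduction, so Appendix A's condition covers it. This is true, but deleting that condition would leave the gap in place, because a closed ulcer still has no wound edge to debride.
- **The plan already looks at missing data and healing.** Section 7 describes missingness, and complete healing is a secondary outcome by arm. Neither says how a healed ulcer enters the primary comparison.

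**Conclusion.** The point holds in a limited form. By the plan's own text, an ulcer closed by T3 has no T3 load, is omitted from the named primary test, still counts as a completer, and is covered by no rule. That the t-test omits such subjects is an inference, but a direct one: the test needs both values and no imputation is specified.

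The size and direction of any bias are unknown. Under the stated assumptions attenuation runs from 0 with no correlation to about 2-25% for correlations of 0.3-0.7 with 5-20% missing in Comparator. If healing is unrelated to change in load, the cost is precision alone. The expectation of 30 subjects for the primary endpoint is not secured by 30 completers. For an exploratory pilot this is a correction worth making before unblinding, not a defect that invalidates the trial.

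**What to change.** 1. **Section 7, primary analysis.** Take the arm difference in T0-to-T3 change from the repeated measures model, with visit as a categorical factor and an arm-by-visit term added, using all available T0, T2 and T3 values. Keep the T3-T0 t-test on available pairs as a sensitivity analysis. State that subjects healed by T2 add no post-baseline load, and that the model relies on the observed loads to account for missing T3 values.
2. **Reporting.** Give, by arm, the number without T3 tissue because of healing, separately from dropout. A rank comparison of all randomised subjects with healed ulcers ranked best is optional. It should be supportive only and labelled as a composite, since it mixes a clinical outcome with a microbiological one.
3. **Sections 4.1 and 7.** State that 15 per arm means completers under 4.4 and that fewer may have a T0-T3 pair.
4. **Appendix A.** Reconcile the 75% area-reduction condition on T3 with 3.2.1, 5.16 and 7. As it stands it would extend the same loss to ulcers that are still open.

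The cost is wording and one model specification, with no new data. The stated number for the primary endpoint becomes slightly less favourable. At this sample size the model may need a simple covariance structure, and Section 7 already warns of convergence problems, so a fallback structure should be named in advance.
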